9.4 DATA SOURCES

Source data will be medical records usually collected during routine clinical practice other than study-specific questionnaires.

Collected variables are defined based on study objectives and according to the non-interventional nature of the study. They consist in data routinely collected in clinical practice, so they are expected to be available in medical charts.

For Charlson Comorbidity Index calculation ICD-9CM will be considered by clinical investigators. If ICD-9CM is not available according to routine clinical practice, main diseases ongoing at baseline will be anyway collected.

The study data will be collected by means of remote data capture using an electronic case report form (eCRF). Investigators will be provided a user-friendly paper form which is intended as a supportive tool for data collection and will be filled in according to each site specific need (it will not be considered as a source data).

Patient-reported outcomes, i.e. scales and questionnaires, will be collected on paper and they will constitute source data.

9.5 STUDY SIZE

The sample size was determined on the basis of feasibility criteria. In fact, according to the volume of patients managed by the centres involved in this study, inclusion of 400 subjects (20 patients/center) with the characteristics defined at Inclusion/Exclusion criteria paragraphs is deemed reasonable for the planned enrolment period (8 months). Assuming a drop-out rate ranging from of 5% to 20% (including not evaluable,lost-to follow up and not on treatment patients), effective sample size is expected to range between 320 (drop out=20%) and 380 (drop out=5%).

An evaluation of the possible achievable precision of the estimates was performed considering the primary objective of the study. No data on treatment satisfaction is available about COPD patients specifically, therefore available literature data was used as a reference to evaluate possible scenarios. In particular, literature data about TSQM was found on multiple sclerosis, psoriasis, etc, showing the global satisfaction mean score ranging from 54.4 to 79.7 (17,18)].

Table 2 shows the 95% confidence interval half-width and standard error (SE) of the expected mean of global satisfaction score under different sample sizes.

| | | | | |
|------------------------------------|-------------|-------|-------------|-------|
| Expected Mean (SD) | 54.4 (21.4) | | 79.7 (16.6) | |
| Sample Size | 380 | 320 | 380 | 320 |
| 95% confidence interval half width | 2.152 | 2.345 | 1.669 | 1.819 |
| Standard error (SE) | 1.098 | 1.196 | 0.852 | 0.928 |

Table 2. 95% confidence interval (CI) half-width and standard error (SE) of the expected mean assuming N=380/320 evaluable patients [19]

In all considered scenarios the relative error of the estimate (CI half-width/expected mean) is lower than 30%. The lower the sample size and the higher the standard deviation, the lower the estimate precision.

9.6 DATA MANAGEMENT

The CROs in charge of the study is [REDACTED].

The data entered into the eCRFs by investigational staff will be reviewed for completeness and accuracy and the site personnel will be instructed to data entry data into the eCRFs and to make any required corrections or additions. In order to validate the e-CRF content a qualitative pre-test will be performed, by simulating data capture during study conduction.

The Data Manager will perform the cleaning session by running post-entry checks by means of validation programs and data listings specific for the study. During this process, if clarifications are needed, the Data Manager will raise queries by means of data query forms

through the application. Designated investigator site staff is required to respond to the query and make the correction to the database.

Patients violating inclusion/exclusion criteria will not be considered for analyses. A description of reasons of violation will be provided anyway. After these actions have been completed and the database has been declared to be completed and accurate, it will be locked and made available for data analysis. Any changes to the database after that time can only be made by joint written agreement between the Medical Adviser, the Trial Statistician and the Data Manager. Only authorized and well-documented updates to the study data will be possible after database lock.

Each participating site will maintain appropriate medical and research records for this study, in compliance with GPP and regulatory and institutional requirements for the protection of confidentiality of subjects.

Patient initials or names will not be recorded in the database: patients will be associated to a unique identifier, assigned as a progressive number within each site. Due to the observational nature of the study no independent review of the data will be performed.

Data access rules, as well as data transfer to Sponsor, will be detailed in the Data Management Plan.

9.7 DATA ANALYSIS

Descriptive analysis will be means, medians, quantiles, proportions (with their respective 95% confidence intervals and SE when relevant) and contingency tables according to the nature of the variables. As a dispersion measurement the standard deviation and the interquartile range will be calculated.

Statistical analysis will be performed using the SAS software.

The statistical analysis will be done on all evaluable patients i.e. patients who enter the study without inclusion-exclusion criteria violations and with at least one TSQM-9 domain score (effectiveness, convenience and global satisfaction) calculated. Enrolled patients not evaluable for analysis will be described in terms of frequency of violations and according main socio-demographic variables (such as age and gender), clinical (such as disease severity and number of exacerbations in the 12-month before enrollment) and treatment satisfaction scores (if available) at baseline.

Patients with missing values will not be excluded from the analysis, their data will not be replaced; frequency of missing data will be given for all analyzed variables. Lost to follow up patients will be analyzed until their last available visit.

Appropriate descriptive statistics for main socio-demographic (gender, age, race, education and employment status, smoking habits) and clinical variables (medical history for COPD and not, disease severity and awareness) at baseline visit will be presented to describe the study population at inclusion. Patients at inclusion in the study will be also described in terms of ongoing pharmacological and non pharmacological treatments for COPD.

Moreover, the study population will be described in terms of number of exacerbations occurred during study period and changes in COPD medication since baseline.

The study objectives will be evaluated as below described.

Primary objective

The patients' satisfaction for medical treatment will be assessed by the 9-item Treatment Satisfaction Questionnaire for Medication (TSQM-9) at each study visit (45, 46). TSQM-9 is a self-rated tool for evaluating patient satisfaction to medical therapy. It is composed by 3 domains covering efficacy, convenience and global treatment satisfaction. TSQM-9 scores will be calculated according to author's instructions and summarized at each time point on all evaluable patients. Patients lost to follow up will be considered until their last available visit.

The patients switching treatment during observation period will not be excluded from analysis and will be evaluated at each visit as above described. Few patients are expected to stop treatment during study; if any, for primary objective evaluation they will be censored at the latest available visit. Comparisons of satisfaction between different treatment/devices are not matter of this study, throughout all analysis treatments will be lumped together.

Secondary objectives

#1 To describe patient disease perception (B-IPQ), adherence to COPD treatment (MMAS4), health status (CAT) and dyspnea (MMRC) during a 12-month observation period

A description of B-IPQ (consequences, timeline, personal control, treatment control, identity, concern, emotions and illness comprehensibility), MMAS-4, CAT and MMRC scores will be provided at baseline and at follow-up visits. Scale scores will be summarized at each time point. Patients lost to follow up will be considered until their last available visit. Missing items of questionnaires/scales will be replaced if applicable according to scoring algorithm [32-38].

#2 To analyse the relation between treatment satisfaction for medical treatment and demographic/clinical parameters and PROs during a 12-month observation period

Three regression models (one for each TSQM-9 domain score) will be estimated; the dependent variable will be domain score and the independent ones will be: age and gender (at enrollment), number of exacerbations, relevant spirometry parameters (such as FEV1, FVC, FEV1 % of the predicted, RV, TLC, DLCO), level of dyspnea (MMRC score), impact of COPD on a patient's life (CAT) and treatment adherence (MMAS-4 score) collected during observational period. Because dependent variable will be collected at each study visit, repeated measures models will be estimated taking into account all available values for dependent and independent variables. Patients could be classified in mild or moderate/severe according to lung function parameters. This will allow to evaluate treatment satisfaction in different groups of patients.

The patients switching treatment during observation period will not be excluded from analysis and will be evaluated at each visit. The patients stopping treatment during study will be censored at last available visit.

#3 To describe the health care resources utilization and related cost during a 12-month observation period

The health care resources consumption will take into consideration the following events related to management of COPD and COPD exacerbations: inpatients and outpatients hospitalization (inward and day-hospital), accesses to emergency room, General Practitioner (GP) and outpatient visits, laboratory tests and examinations, pharmacological (LABA, LAMA, SABA, SAMA, ICS/LABA, steroids, antibiotics, long-Term Oxygen Therapy, etc.) and non-pharmacological therapies (pulmonary rehabilitation) occurred/administered during study period.

Medications for adverse events will be considered too.

The annual direct health care resource consumption and related cost will be provided by means of descriptive statistics of the variables mentioned above. In order to describe the health care cost from enrolment up to the end of 12-month follow-up according to the INHS point of view (26), a two steps approach will be followed: (i) first of all the resource consumed since enrolment will be calculated and then (ii) a monetary value will be assigned to the resource consumption.

(i) Health care resources consumption exclusively related to COPD, COPD exacerbations and COPD-drug-related adverse events will be computed during observational period in terms of pharmacological and non-pharmacological treatments, number of (inward and day-hospital) hospitalizations, number of emergency room accesses, number of GP visits, specialist visits, laboratory tests or examinations (spirometry, FEV1, FVC, FEV1 % of the predicted, RV, IC, TLC, DLCO).

(ii) In order to estimate the economic impact on health care sector related cost (30) of the above mentioned health services (hospital admissions, visits, treatments, examinations, spirometry) consumption, a monetary value to each event recorded will be assigned, as defined by the Italian Ministry of Health through the tariffs in force for outpatient setting (31). The cost of hospitalization will be valued according to the most recent available diagnosis-related group (DRG) tariffs (32); finally, pharmacological treatments will be costed at consumer price. All costs will be expressed in €2015. A monthly (or yearly) cost will be provided by taking into account patients according to duration of observation and parametrizing each patient to the 12-month observation period.

Descriptive statistics (mean, standard deviation, median, minimum and maximum) of the annual direct health care resource consumption and related cost will be provided.

Non-parametric bootstrap method will be applied to cost data for calculating 95% confidence intervals (22-23).

A multiple linear regression model will be performed to investigate statistical significance of INHS cost predictors (24).

#4 To assess the correlation between patients' satisfaction and resource utilization.

Correlation indexes will be calculated between treatment satisfaction domain scores of TSQM-9 and healthcare resource consumption (such as number of hospitalizations, emergency room accesses, GP visits, laboratory test. etc... during observation period) at 12-month follow-up visit. The patients switching treatment during observation period will not be excluded from analysis and will be evaluated at each visit. The patients stopping treatment during study will be censored at their last available visit.

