9.13 LIMITATIONS OF THE RESEARCH METHODS

This is a non-interventional (observational) study which puts patients under observation for one year prospectively. However information, selection and/or recall bias have to be taken into account, as in all non-interventional studies.

Investigators could select patients in order to enroll those ones who most probably will be followed up or most probably correctly understand the questionnaires (selection bias). In order to limit this bias, monitoring visits could be randomly performed in sites to verify whether enrolment was performed consecutively.

The information to be captured is usually recorded in medical charts or on questionnaires filled in during visit: this also should limit recall bias of information.

As regards confounding, the primary aim of the study is to evaluate the patients' satisfaction for medical treatment irrespective of the ongoing treatment, no causality nor associations to treatments will be evaluated because of the lack of a control group. The regression models to analyze the relation between treatment satisfaction scores and demographic, clinical and PROs parameters during a 12-month observation (secondary objective #2) will provide adjusted estimates of the impact on satisfaction scores of each variable keeping constant the others included in the models.

Patients with missing values will not be excluded from the analysis, their data will not be replaced; frequency of missing data will be given for all analyzed variables. Patients with missing and not missing values in TSQM9 domain scores will be described according to main socio-demographic and clinical features.

As far as generalizability of results, the study aims to provide information on COPD patients enrolled in the study; it does not mean to be generalized to the population of Italian COPD patients, because sites are selected. However sampling is based on consecutive enrolment, in order to avoid patient selection during recruitment.

Finally, target sample size is considered to be achievable during the enrolment period on the basis of preliminary feasibility considerations.

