4.1 Patient disposition

Table 1. Enrolled and evaluable patients

The table will provide absolute and relative frequencies of:

- patients enrolled in the SAT study
- patients evaluable for safety analysis (Safety set) (as described in par. 2.4)
- patients evaluable at enrollment (Full analysis set) (as described in par. 2.1)
- patients evaluable at enrollment and at 6 month follow-up visit (as described in par. 2.2)
- patients evaluable at enrollment and at 12 month follow-up visit (as described in par. 2.3)

The percentages will be computed over the total number of enrolled patients.

Table 2. Reasons for non-eligibility to analyses

The table will describe the reasons for patient non-eligibility.

Absolute and relative frequency distribution will be performed; the percentages will be computed out of the total number of enrolled patients.

Table 3. Premature study termination

The table will describe the distribution of patients withdrawn from the study (“Did the patient complete the study?” [\[F18_STUDY_COMPLETION.SC_1\]](#) = “No”); moreover, absolute and relative frequency of reasons for premature study termination (“Cause of drop out” [\[F18_STUDY_COMPLETION.SC_2\]](#)) will be provided.

Percentages will be computed out of the total number of enrolled patients.

The distribution of patients withdrawn for other reasons will be also reported in a separate table (“If other cause, specify:” ≠ missing [\[F18_STUDY_COMPLETION.SC_3\]](#)), if other reason frequency is >20%.

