- Main descriptive statistics (mean, median, standard deviation, quartiles, min, max) of patients' values of DLCO at enrollment [F07_FUNCTIONAL_ASSESSMENT.FA_DLCO_Num], along with the respective DLCO unit [F07_FUNCTIONAL_ASSESSMENT.FA_DLCO_unit].

Descriptives will be computed out of the total number of FAS patients.

During data analysis, the Biostatistician will evaluate to perform the analyses described above also considering the evaluable patients at 6 months and/or at 12 months, depending on the number of patients of these analysis sets (in case the number of patients for these two analysis sets is relevantly different from the number of FAS patients), in order to understand if a selection bias is present.

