4.3 Patients' satisfaction for medical treatment (TSQM-9) (primary objective)

Table 10. Patients' satisfaction for medical treatment (TSQM-9 items) at each study visit

The table will provide absolute and relative frequency of patients' answers to TSQM-9 items (see Appendix 8.3) at each study visit.

Percentages will be calculated over the number of patients respectively evaluable at the time point considered, namely at enrollment (i.e. FAS patients), at 6 months (i.e. evaluable patients at 6 months) and at 12 months (i.e. evaluable patients at 12 months).

Table 11. Patients' satisfaction for medical treatment (TSQM-9 subscales) at each study visit

The table will provide the descriptive statistics (mean, median, standard deviation, quartiles, min, max) of the TSQM-9 subscales scores (as defined in "Computed variables" chapter) at each study visit.

Changes from enrollment in TSQM-9 subscales scores (see 'Computed variables' chapter) will be also summarized by visit.

95% confidence intervals limits of the mean will be provided for each estimate (i.e. TSQM-9 subscales scores and changes). Descriptives will be calculated over the number of patients respectively evaluable at the time point considered, namely at enrollment (i.e. FAS patients), at 6 months (i.e. evaluable patients at 6 months) and at 12 months (i.e. evaluable patients at 12 months).

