7 REVISION HISTORY

| Table (N° and title) | SAP version and date | Change description | Applicant | Note |
|-----------------------|-----------------------|--|-----------------------|------|
| All applicable tables | Vers. 1.0, 16/09/2016 | Analysis modified according to the changes agreed with Sponsor during the conference call held on the 27/09/2016 | BI | |
| All applicable tables | Vers. 1.0, 16/09/2016 | General review of the document and proposed analyses | [REDACTED] | |
| Whole document | Vers. 1.1, 10/07/2017 | General review of the document | BI Global | |
| Tables 4-6 | Vers. 1.2, 25/07/2017 | Descriptive analyses on non-evaluable patients removed | BI Global | |
| Tables 20-22 | Vers. 1.2, 25/07/2017 | Regression model characteristics further specified | BI Global, [REDACTED] | |
| Whole document | Vers. 1.3, 15/09/2017 | General review of the document | BI Global | |
| Table 14 | Vers. 1.4, 21/09/2017 | Analysis on CAT score categories added | BI Global | |

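### The SAP omits the protocol's descriptions of non-evaluable patients and of missing TSQM-9 scores, so selective loss need not be shown and is not reduced in the 6- and 12-month means

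*Protocol*

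**What the plan says.** The protocol makes two commitments. In 9.13, as part of its answer to missing data: "Patients with missing and not missing values in TSQM9 domain scores will be described according to main socio-demographic and clinical features". In 9.7: "Enrolled patients not evaluable for analysis will be described in terms of frequency of violations and according main socio-demographic variables", followed by clinical variables and baseline satisfaction scores where available. Evaluable patients are defined in 9.7 as "patients who enter the study without inclusion-exclusion criteria violations and with at least one TSQM-9 domain score" calculated.

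The SAP's list of Tables 1 to 46 has no table for either commitment. Tables 4 to 9 (SAP 4.2) describe the FAS only. On patients left out, SAP 4.1 keeps counts (Table 1), reasons for early termination (Table 3) and, in Table 2: "The table will describe the reasons for patient non-eligibility". The revision history in SAP section 7 has the entry "Descriptive analyses on non-evaluable patients removed", which suggests that the omission was deliberate.

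SAP 4.2 retains one check: "the Biostatistician will evaluate to perform the analyses described above also considering the evaluable patients at 6 months and/or at 12 months", depending on whether those sets differ notably in size from the FAS, "in order to understand if a selection bias is present". No figure defines a notable difference.

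For the primary objective, SAP 4.3 says of Table 11: "Descriptives will be calculated over the number of patients respectively evaluable at the time point considered". That means the FAS at enrolment, the 6-month set at 6 months and the 12-month set at 12 months. Table 11 also gives within-patient changes from enrolment, with 95% confidence intervals. SAP section 4 rules out imputation. The mixed models in SAP 4.9 are restricted to patients evaluable at 12 months.

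**The concern.** The primary objective is the level of satisfaction at enrolment, 6 and 12 months. If patients who are missing at a later visit would have scored differently from those seen, the later mean moves for that reason alone. The protocol gives grounds to expect a link. Its section 7 says satisfaction affects how likely patients are to continue their medication, and 9.7 censors patients who stop treatment for the primary objective. The 6- and 12-month sets also leave out visits outside 5 to 7 and 11 to 13 months, and visits with no computable TSQM-9 domain score.

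The protocol's safeguard is descriptive: show who is missing and how they differ. Without it, a reader of Table 11 cannot judge whether a steady or rising 12-month level describes the cohort or only those who remained.

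**Working it through.** **1. The commitments against the SAP**

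| Protocol commitment | SAP |
|---|---|
| 9.13: patients with and without TSQM-9 scores, by socio-demographic and clinical features | No table; optional repeat of Tables 4 to 9 in the 6- and/or 12-month sets |
| 9.7: non-evaluable patients, by violations, baseline features and baseline TSQM-9 | Reasons only (Table 2); no characteristics |

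The two commitments cover different patients. Under the 9.7 definition, a patient with a baseline score who later leaves is still evaluable, so the 9.7 sentence covers entry violators and patients with no score. Later loss falls under 9.13.

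**2. What the SAP 4.2 check could show**

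It repeats Tables 4 to 9, and none of these holds baseline TSQM-9. It also compares a subset with the whole:

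mean(retained) − mean(FAS) = share lost × [mean(retained) − mean(lost)].

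At 20% loss, a 10-point difference between retained and lost patients appears as 0.20 × 10 = 2 points.

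**3. The protocol's precision figures (9.5, Table 2)**

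Effective n = 400 × (1 − drop-out): 400 × 0.80 = 320 and 400 × 0.95 = 380. SE = SD/√n; half-width = 1.96 × SE.

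| SD | n | SE | Half-width |
|---|---|---|---|
| 21.4 | 380 | 1.098 | 2.152 |
| 21.4 | 320 | 1.196 | 2.345 |
| 16.6 | 380 | 0.852 | 1.669 |
| 16.6 | 320 | 0.928 | 1.819 |

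All agree with the protocol. They cover sampling error only.

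**4. Size of a possible shift**

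Bias of the 12-month mean = share of FAS lost × gap, where the gap is the difference in 12-month mean between retained and lost patients. The documents give no gap, so 5, 10 and 15 points are assumptions.

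The share lost is also uncertain. The protocol's 5% to 20% combines patients lost to follow-up with those not evaluable or not on treatment. Patients excluded at entry never join the FAS, so 20% is the upper bound of the planning range. If half of the 80 were entry exclusions (an assumption), the FAS is 400 − 40 = 360 and the loss is 40/360 = 11.1%.

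| Share of FAS lost | Gap 5 | Gap 10 | Gap 15 |
|---|---|---|---|
| 5% | 0.25 | 0.5 | 0.75 |
| 11.1% | 0.6 | 1.1 | 1.7 |
| 20% | 1.0 | 2.0 | 3.0 |

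At 20% loss the bias equals the half-width at a gap of 2.345/0.20 = 11.7 points (SD 21.4) or 1.819/0.20 = 9.1 points (SD 16.6).

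Coverage of the nominal 95% interval is Φ(1.96 − b/SE) − Φ(−1.96 − b/SE), with b the bias. For a 10-point gap it is 61% (SD 21.4) or 42% (SD 16.6) at 20% loss, and 93% or 91% at 5% loss.

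**5. Whether any planned analysis reduces the shift**

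Table 11 uses available cases. The paired changes compare each patient with themselves, which removes the effect of changing composition, but only for patients with scores at both visits. The mixed models leave out the earlier scores of anyone not evaluable at 12 months, although Protocol 9.7 asks for all available values. No planned analysis uses the earlier scores of lost patients to estimate the later levels.

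**The case against.** The study is descriptive, the protocol says missing values will not be replaced, and 9.13 disclaims generalisation to Italian COPD patients. Tables 1 to 3 show how many are lost and why, and SAP 4.2 names selection bias as the purpose of its check. If less satisfied patients leave and nothing else changes, the paired changes in Table 11 would be near zero, which exposes a rise in the raw mean as compositional. A repeated-measures model on all FAS patients rests on data being missing at random. That fails if patients leave because of dissatisfaction never recorded, and the model may project scores for patients who have stopped treatment.

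Much of this stands. A reader might infer that the SAP has no check on selective loss, that dropping the 9.7 description is what conceals 12-month drop-out, or that each visit's set is nested in the one before. The documents support none of these. The 4.2 check exists, though it is weak. The 9.7 sentence does not cover later leavers who have a baseline score. The 12-month set must meet the FAS criteria but need not be evaluable at 6 months.

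The objection does not dispose of two things. The 9.13 commitment has no required table, and the SAP does not acknowledge the departure, whereas SAP 4.9 openly states its departure on covariates. And the paired changes do not repair the 6- and 12-month levels, which are the primary objective.

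**Conclusion.** The point holds as a gap between protocol and SAP. Two promised descriptions have no table. The remaining check is discretionary, diluted and lacks baseline TSQM-9. No planned analysis reduces the effect of selective loss on the visit means.

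The size is conditional. With an assumed 10-point gap, the shift runs from 0.5 point at 5% loss through about 1.1 at 11% to 2.0 at 20%, against stated half-widths of 1.669 to 2.345. It is negligible at the low end and comparable to the sampling error at the high end. A reader might infer that the 12-month mean will be biased, or that a stable mean would be an artefact. The documents do not support that, because they give neither the loss from the FAS nor any difference between lost and retained patients. What is missing is the means to tell which case applies. The point merits correction but does not undermine the design.

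**What to change.** 1. Make the SAP 4.2 check mandatory, as one table of FAS baseline age, gender, severity, prior-year exacerbations and baseline TSQM-9 domain scores, by evaluable yes/no at 6 and at 12 months. Restore the short baseline description of patients excluded from the FAS. If either is still to be omitted, state the departure and the reason in the SAP.

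2. As a sensitivity analysis beside the observed means in Table 11, report visit means and changes from a repeated-measures model (visit as a factor, unstructured covariance) on all FAS patients with any score for that domain. State that it assumes data are missing at random, and how scores after treatment stop are handled, consistent with the protocol's censoring rule.

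Both use data already collected and leave the primary definition unchanged. The cost is one extra table, a short description of excluded patients, and a second set of visit means to explain. The model is not a cure: its means are only as good as the missing-at-random assumption.
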